Observational Study Participants: The study will include men and women aged 45–64 who are residents of Kaunas City and live in private apartments. Approximately 1,000 individuals will be randomly selected. Individuals living in institutions, rented accommodations, or nursing homes will be excluded from the study.

Experimental Clinical Trial Participants – Inclusion Criteria: Participants must be aged 45–64, male or female, residents of Kaunas City, and randomly selected from the observational study cohort. They must agree to wear a smart wristband sensor for 7 days and sign an informed consent form to participate in the healthy lifestyle intervention. A total of 180 participants will be enrolled.

Exclusion Criteria for Clinical Trial: Participants will be excluded if they have unstable angina, cardiomyopathy, hypertension with blood pressure greater than 160/110 mmHg, cardiac pacemakers, neurological diseases, alcohol dependence, limited mobility, or if they are pregnant.

Justification for Sample Size: The experimental clinical trial involving 180 participants will be conducted by researchers at VMU. The trial will assess the impact of a healthy lifestyle on early metabolic responses (biomarkers and health risks), considering individual PM0.1 exposure levels. To enhance data reliability and reducing the risk of Type I error (false positive) the confidence level is set up at 99.9%. The sample size was calculated using the formula:

$$N=2\times(Z_{1-\alpha/2}+Z_{1-\beta}/\delta_0)^2 \times p \times (1-p),$$

Where:

- N = required sample size
- $Z_{1-\alpha/2} = 3.29$ (for a 0.1% significance level)
- $Z_{1-\beta} = 0.842$ (for 80% statistical power)
- $\delta_0 = \text{effect size} = 0.1$
- $p = \text{expected proportion} = 0.3$

This gives:

$$N \approx 2 \times (3.29 + 0.842 / 0.1)^2 \times 0.3 \times 0.7 \approx 58 \text{ participants}$$

To account for potential dropouts (e.g., due to acute infections), a sample size of 60 per group is proposed. Therefore, a total of 180 participants will be enrolled in the clinical trial.

8. Biomedical Research Methodology

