Experimental Clinical Trial: Participants who completed the online survey and conform to the study inclusion criteria will be eligible. Those interested in participating in the healthy lifestyle clinical trial can contact the researchers via the details provided in the internet survey form. Upon contact, participants will be asked to updated information on waist circumference, blood pressure, and address. Eligible participants will be invited to the Family Medicine Clinic of Kaunas Clinics at the Lithuanian University of Health Sciences (LSMU).

Inclusion criteria: Age 45–64, residence in Kaunas City on streets with identified high air pollution levels, and self-reported metabolic disorder indicators such as increased waist circumference and/or elevated blood pressure. Following contact, appointment times will be coordinated. At the initial visit, researchers will review the participant's health status. Participants will be informed about the experimental clinical trial and will sign an informed consent form. They will then be randomly assigned to one of three healthy lifestyle groups and instructed on their 7-day health behaviour study. Groups: 1. Control group (usual routine); 2. Physical activity in green space (daily 30-minute brisk walk); 3. Mediterranean diet intervention.

All groups' participants health assessments will be conducted by family doctor on Day 1 and Day 8 using certified medical equipment. Participants will be asked to arrive fasting or having not eaten for at least 2 hours before their visit.

Procedures will include:

- Blood sampling (up to 20 ml) for analysis of metabolic biomarkers
- Blood pressure measurement
- Waist circumference measurement
- Body composition analysis

All participants will wear Fitbit Alta wristband sensors for 7 days, which will collect digital data on physical activity (METs), step count, heart rate, sleep quality. Collected data will be transferred to a secure digital platform and coded to assess the results.

[figure not shown]

Fig. 1 Scheme of the Kaunas Clinical study

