Each group's clinical health indices and metabolic responses will be assessed by measurements blood pressure, waist circumference, high-density lipoproteins (HDL), triglycerides, plasma glucose levels, also metabolomic, proteomic, and DNA methylation biomarkers before and after the 7-day intervention. Primary proteomics screening comprises of 4–6 oxidative stress and inflammation markers via immunoblotting. In a second phase, based on the initial results, advanced OMICs analysis will be conducted using high-resolution techniques, such as redox/phospho-proteomics, metabolomics, DNA methylation via EPIC chip (for genome-wide methylation analysis). All data will be analysed using mathematical modelling to account for confounding variables. Results will substantiate recommendations for reducing metabolic disorder risks, targeted to healthcare professionals and the public.

Data Analysis and Evaluation: Both the observational and experimental clinical studies will use a standardized exposure–health response analysis approach. Key methods: multivariate logistic regression analysis, adjustment for confounding factors using mathematical modelling to estimate the strengths of the relationship and 95% confidence intervals between the variables.

Biological samples for metabolic response analysis will be sent to accredited partner laboratories:

- DNA methylation analysis: National Center of Pathology (Lithuania), Laboratoire National de Santé (Luxembourg)
- Proteomic analysis: University of Southern Denmark (Odense, Denmark)

- Metabolomic analysis: Institute for Molecular Sciences, University of Eastern Finland (Finland)

9. Description of Study Sites and Institutions Involved in Biomedical Research Activities

The METSGREEN biomedical research is being conducted together with 15 international scientific MARKOPOLY project centres, as part of an international collaboration. The participating institutions are:

1. Universitätsmedizin der Johannes Gutenberg-Universität Mainz (Germany) – *Coordinator*
2. Università degli Studi di Padova (Italy)
3. Medical University of South Carolina (United States)
4. Vytautas Magnus University (Lithuania)
5. University of Belgrade, Faculty of Medicine (Serbia)
6. The Cyprus Institute (Cyprus)
7. Concentris research management gmbh (Germany)
8. Max Planck Society for the Advancement of Science (Germany)
9. Laboratoire National de Santé (Luxembourg)
10. Luxembourg Institute of Health (LIH) (Luxembourg)

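### The only outcome model named for the randomised trial is logistic regression, which fits its continuous Day 1/Day 8 clinical outcomes badly, and no yes/no trial event is defined

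*Protocol*

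**What the plan says.** Under Data Analysis and Evaluation in section 8, the protocol states: "Both the observational and experimental clinical studies will use a standardized exposure–health response analysis approach". The next sentence gives the methods: "Key methods: multivariate logistic regression analysis, adjustment for confounding factors using mathematical modelling". Results are to carry 95% confidence intervals. No other outcome model is named in the protocol. Land-use regression (section 5) models exposure, and the mathematical modelling mentioned elsewhere in section 8 has no stated form.

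The trial outcomes are described earlier in section 8: "Each group's clinical health indices and metabolic responses will be assessed by measurements blood pressure, waist circumference", followed by HDL, triglycerides, glucose and omics markers, before and after the 7-day intervention. Health assessments in all groups "will be conducted by family doctor on Day 1 and Day 8 using certified medical equipment". Section 5 lists the same clinical measures as secondary endpoints. Allocation is 1:1:1 to control, walking in green space, or Mediterranean diet.

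Section 7 gives the trial's purpose: "The trial will assess the impact of a healthy lifestyle on early metabolic responses (biomarkers and health risks), considering individual PM0.1 exposure levels". The sample-size calculation uses an "expected proportion" of 0.3 and an effect size of 0.1 without saying what event the proportion refers to, and concludes that "a sample size of 60 per group is proposed".

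**The concern.** Logistic regression needs a yes/no outcome. It suits survey items such as physician-diagnosed disease. The trial's clinical outcomes are measurements, and the protocol sets no threshold, responder rule or Day 8 syndrome status as a trial endpoint. Section 6 lists the metabolic-syndrome criteria, but as background and without cut-offs.

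Taken at its word, the named model could be used in the trial only after each measurement had been cut at a point that the protocol does not define. Two things would be at stake. With about 60 per arm, much of the information on the walk and diet effects would be lost. And with five measures that could each be cut in several places, the choice could be made after the data are seen. Section 8 says the results will support recommendations to professionals and the public, so the efficiency of the arm comparison matters.

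**Working it through.** **Inputs from the protocol.** 60 per group, p = 0.3, effect size 0.1, 80% power (Z = 0.842), two-sided 0.1% level (Z = 3.29), all from section 7. Continuous outcomes on Day 1 and Day 8 from sections 5 and 8.

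**Inputs assumed.** A roughly normal outcome; Day 1–Day 8 correlation r between 0.5 and 0.8; a cut with 20%, 30% or 50% of participants above it. The protocol gives no standard deviation, correlation, cut or target difference on a measured scale.

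**The protocol's own figure.** The printed expression gives 2 × (3.29 + 0.842/0.1)² × 0.3 × 0.7 = 2 × 11.71² × 0.21 = 57.6, which is the stated 58. The sizing is therefore in terms of a proportion. How the formula is bracketed is a separate matter and is not used here.

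**Information kept after a cut, no Day 1 adjustment.** The fraction is φ(c)²/[p(1−p)], where c is the cut on the standard normal scale.
- p = 0.5: 0.3989²/0.25 = 0.637
- p = 0.3 (or 0.7): 0.3477²/0.21 = 0.576
- p = 0.2: 0.2800²/0.16 = 0.490

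**Information kept when both models adjust for Day 1.** The fraction is the average over a standard normal x of φ(u)²/[Φ(u)(1−Φ(u))], with u = (r·x − c)/√(1−r²).

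| Above the cut | r = 0.5 | r = 0.7 | r = 0.8 | 60 per arm works like |
|---|---|---|---|---|
| 50% | 0.570 | 0.485 | 0.415 | 34 to 25 |
| 30% (or 70%) | 0.510 | 0.430 | 0.366 | 31 to 22 |
| 20% | 0.428 | 0.355 | 0.300 | 26 to 18 |

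For cuts of 30% to 50%, the smallest loss is 1 − 0.570 = 43% and the largest is 1 − 0.366 = 63%.

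**Illustration with the protocol's own numbers.** Assume that 0.1 means a fall from 30% to 20% between two arms. On a normal scale that is a shift of 0.842 − 0.524 = 0.317 SD (from unrounded values). In simulations of 60 v 60 (6,000 runs per setting, r = 0.5/0.7/0.8, 5% level), power was:
- linear model with Day 1: 0.496/0.671/0.817
- logistic model with Day 1: 0.282/0.333/0.384

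At the 0.1% level the figures were 0.088/0.181/0.310 and 0.031/0.037/0.053. The linear model does better, but most of these values are below 80%, so this illustrates the gap and does not show that the trial is adequately powered.

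**Effect of skew.** The gain depends on scale. With strong right skew (assumed log-scale SD 1.0, r = 0.5, shift of 0.4 SD on the log scale), a linear model of raw values had 49% power. A logistic model at a 50% cut, adjusted for log Day 1, had 48%. With log-scale SD 0.5 the figures were 62% and 46%. Right-skewed measures therefore need a log scale to keep the advantage.

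**Difference detectable with a continuous outcome.** The formula is (Zα + Zβ) × √(2(1−r²)/60).
- 0.1% level, no Day 1: 4.132 × √(2/60) = 0.75 SD
- 5% level, no Day 1: 2.802 × √(2/60) = 0.51 SD
- with Day 1, r = 0.5 to 0.8: 0.65 to 0.45 SD at 0.1%, and 0.44 to 0.31 SD at 5%

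**The case against.** The methods sentence speaks of key methods, not of the sole method, and refers to mathematical modelling in general terms. The trial data also include proteomic, metabolomic and methylation measurements, for which a logistic-only reading is doubtful. A reader might infer that the protocol commits the sponsor to cutting blood pressure, waist, HDL, triglycerides and glucose into yes/no. It does not: no passage says so, and the loss arises only if the named model is applied to them. This stands, and it limits the finding.

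A missing cut-off, or the lack of an explicit between-arm comparison, could also be left to a statistical analysis plan that is not shown. That is fair for the omissions taken alone. What remains is not an omission: the protocol names a model, applies it expressly to the trial, and that model does not match the trial's listed clinical outcomes.

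A coherent binary reading is possible. The sizing uses a proportion, the stated aims mention risk, and section 6 lists categorical syndrome criteria. On that reading logistic regression would match the sizing, and the defect would be an unnamed event. The documents do not settle this, so the sizing text should not be replaced outright.

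Finally, the size of the loss rests on assumed normality, correlation and cut. This also stands; strong skew can remove the advantage of a linear model on raw values.

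**Conclusion.** The point holds in a conditional form. The one outcome model that the protocol names for the trial is ill-suited to the clinical outcomes that it lists, and the event that the model would need is not defined. If it is applied to those outcomes, about 43% to 63% of the information is lost at a 30% to 50% cut. That range holds for a roughly normal outcome, with both models adjusted for Day 1 and an assumed correlation of 0.5 to 0.8.

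The documents support neither the claim that dichotomisation is planned nor the claim that a linear model would make the trial adequately powered. The change should be made, but it is not critical: the trial endpoints are labelled secondary and the wording leaves room for suitable models.

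**What to change.** **Section 8, Data Analysis and Evaluation.** Add text such as: *In the trial, blood pressure, waist circumference, HDL, triglycerides and glucose will each be analysed by a linear model of the Day 8 value on randomised group and the Day 1 value of the same measure (log scale for right-skewed measures such as triglycerides), with participants analysed as assigned. Walk-minus-control and diet-minus-control differences will be reported with confidence intervals.*

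Keep the PM0.1 association in the trial as a separate analysis, labelled observational, with PM0.1 as a continuous term. Keep logistic regression for binary survey outcomes such as physician-diagnosed disease. The omics markers are outside this change.

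**Section 7, Justification for Sample Size.** Make the sizing basis match the analysis.
- If a yes/no trial event lies behind p = 0.3, name it and keep logistic regression for that event.
- Only if there is none, restate the sizing as the SD difference detectable with about 60 per arm at 80% power, at the significance level that the sponsor will actually use. Section 7 says "the confidence level is set up at 99.9" per cent, while section 8 reports 95% intervals. Without Day 1 adjustment the detectable difference is about 0.75 SD at the 0.1% level or 0.51 SD at 5%; it is smaller with adjustment.

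**Cost.** No extra participants or measurements, since both visits are already planned. The section 8 change is wording. In section 7 the sponsor must either name an event or change the basis of the sizing. The downside is that trial results become mean differences (ratios for logged measures), which are not on the survey's odds-ratio scale.

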Measured concentrations of PM0.1 and noise levels in 20 locations across the city of Kaunas. Using a land-use regression (LUR) model, exposure levels for 1,000 participants will be modelled and linked to self-reported health outcomes: prevalence of CVD, blood pressure, waist circumference, and anthropometric data.

Secondary Endpoints:

During the experimental clinical trial (7-day healthy lifestyle intervention), involving 180 participants, key indicators of metabolic disorders will be assessed, including waist circumference and blood pressure measurements, high-density lipoprotein (HDL) levels, triglycerides, plasma glucose concentration, as well as biological markers from metabolomics, proteomics, and DNA methylation. These will be analyzed in relation to environmental exposure, socioeconomic status, and healthy lifestyle factors. Recommendations will be developed for reducing the risk of metabolic disorders.

6. Justification for the Biomedical Research

The international research's "Noise and/or ultrafine particulate matter induced cerebral and cardiovascular damage: novel insights from experimental and epidemiological studies and computational models" (MARKOPOLY) part conducted at Vytautas Magnus University (VMU), title: "Ambient air and noise pollution effect on cardiovascular health risk and lifestyle intervention to attenuate it in 45–64-year population" (METSGREEN), is being conducted to the order of the European Commission, which provides the necessary funding for its implementation. The MARKOPOLY is coordinated by Johannes Gutenberg University in Germany.

Environmental exposures increase health risk factors and account for up to two-thirds of all chronic non-communicable diseases¹. Environmental-related risk factors, among them air pollution, and personal lifestyle habits can contribute to the increase the global burden of CVD such metabolic syndrome, arterial hypertension, and diabetes mellitus. In Europe, approximately 500,000 premature deaths occur annually due to air pollution. However, particulate matter and noise thresholds are not currently incorporated into clinical guidelines. Moreover, the official European environmental pollution limits significantly exceed the standards set by the World Health Organization (WHO). This issue is especially critical for the most vulnerable populations—those affected by social exclusion, chronic illnesses, or advanced age.

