Measures to Reduce Subjective Bias: Participants will be randomly assigned to the three clinical trial groups. Only individuals without the listed health exclusions and who sign informed consent will be included. Assignment to the one of three groups will follow a 1:1:1 ratio. The researcher will handle group allocation and coding. Objective environmental pollution measurements and individual residential exposure will be taken. Seven-day monitoring health outcomes include physical activity, sleep disturbances, heart function. Two health checks will include measurements of blood pressure, body composition, waist circumference, body mass index (BMI) and biomarkers. Blood samples (up to 20 ml) will be collected to analyse metabolic biomarkers.

Mathematical modelling will be used during data analysis. It will control for confounding factors to assess the strength of the exposure–health outcome relationship.

Biomedical Study Plan: The study plan and phases are shown in Figure 1.

Observational Study: A representative sample survey of Kaunas residents will be conducted by a certified survey company that complies with strict personal data security, privacy principles, and legal requirements. In accordance with the General Data Protection Regulation (GDPR), data will be securely stored, lawfully processed, and participants will be able to exercise their rights easily. The internet survey will be conducted using the Google Forms platform, which provides data encryption and access control (limited to authorized personnel). Google services comply with EU data protection regulations, including two-factor authentication, ensuring the confidentiality and security of personal data. Approximately 1,000 individuals aged 45–64 will be included based on their responses to an anonymous online survey, which collects self-reported health indicators (physician-diagnosed chronic diseases), socioeconomic status, and basic residential information.

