Types of Personal Data Collected: In the observational environmental-epidemiological study, data will be collected via an anonymous online questionnaire completed by approximately 1,000 individuals. Collected data will include age, gender, marital status, education level, employment status, monthly income, height, weight, waist circumference, body composition, blood pressure, chronic diseases diagnosed by a physician, smoking status, physical activity, perception of the residential environment, feedback and concerns about the study, and willingness to participate in the 7-day clinical trial. These data will be used to characterize individuals with signs of metabolic disorders for potential inclusion in the experimental clinical study.

For participants of the clinical trial, in addition to the self-reported questionnaire data, the following data will be collected on Days 1 and 8: blood pressure, body composition, heart function, sleep disturbances, physical activity, HDL cholesterol, triglycerides, plasma glucose concentration, and biomarkers from metabolomics, proteomics, and DNA methylation analysis—dependent on particulate matter exposure.

Source of Personal Data: In the observational study, all data are provided voluntarily by participants via the anonymous online questionnaire. In the experimental clinical trial, additional data will be obtained during health assessments and laboratory analysis of blood samples.

Data Coding and Anonymization: All collected data will be coded numerically. Each participant will be assigned a numerical code. Separate databases will be created for coded data and personal-identification data. These databases will be stored on electronic media.

Access to Identifiable Data (Uncoded): Access to identifiable data from the anonymous online survey will be limited to the principal investigator and her designated research colleague, [name], as well as the biomedical centre staff conducting health checks, supervisory bodies (e.g., bioethics committees), and authorized oversight personnel.

Access to Coded Health Data: Coded health data will be accessible only to researchers and scientists preparing scientific publications, reports, and materials for academic and public dissemination, including conferences.

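### Blood-pressure-lowering treatment is not among the listed survey items, so treated readings in a primary-endpoint outcome cannot be corrected; the diagnosis item helps only in part

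*Protocol*

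**What the plan says.** Under Primary Endpoints, Section 5 of the protocol says that modelled exposure for 1,000 participants will be "linked to self-reported health outcomes: prevalence of CVD, blood pressure, waist circumference, and anthropometric data".

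Section 18 (Types of Personal Data Collected) gives the survey content. The list begins "Collected data will include age, gender, marital status, education level, employment status, monthly income, height, weight, waist circumference, body composition, blood pressure" and goes on to "chronic diseases diagnosed by a physician, smoking status, physical activity". It ends with feedback on the study and willingness to join the trial. Section 8 describes the same survey as one that "collects self-reported health indicators (physician-diagnosed chronic diseases), socioeconomic status, and basic residential information". No medication appears in either place.

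For the trial, Section 18 lists as Day 1 and Day 8 data "blood pressure, body composition, heart function, sleep disturbances, physical activity, HDL cholesterol, triglycerides, plasma glucose concentration" and the omics markers, again without medication. Section 5 makes "high-density lipoprotein (HDL) levels, triglycerides, plasma glucose concentration, as well as biological markers" secondary endpoints of the trial, to be analysed in relation to environmental exposure among other factors.

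The trial's exclusion criteria in Section 7 ("Participants will be excluded if they have unstable angina, cardiomyopathy", and further conditions) include a blood pressure limit but do not mention medication, so people on treatment can enter.

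Section 8 names multivariate logistic regression with adjustment for confounding, and one common exposure-response approach for both studies.

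**The concern.** Blood-pressure-lowering drugs are given because pressure is high, and they lower the reading. In a cross-sectional survey, the recorded value in a treated person understates the value that exposure may have helped to raise. If exposure raises pressure, more exposed people cross the level at which treatment starts, and treatment then removes part of the difference under study.

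Randomisation gives no protection here, because the primary objective (Section 3) is an observational association. The gap is also one of data collection rather than analysis. Section 11 says that most respondents take part once, in an anonymous questionnaire, so a later analysis plan cannot recover a treatment status that was never asked.

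The same reasoning reaches part of the trial. Its arms are randomised, but exposure is not. Section 3 lists the association of ultrafine particles with metabolic syndrome indicators among the trial's objectives, so lipid- and glucose-lowering treatment bears on those exposure analyses.

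**Working it through.** **1. What is collected against what is analysed**

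| Study | Outcome related to exposure | Relevant treatment | Treatment listed? | Nearest item listed |
|---|---|---|---|---|
| Survey, about 1,000 | self-reported blood pressure | blood-pressure-lowering | no | physician-diagnosed chronic disease |
| Trial, 180 | measured blood pressure | blood-pressure-lowering | no | same questionnaire item |
| Trial, 180 | HDL, triglycerides, glucose | lipid- and glucose-lowering | no | same questionnaire item |

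Lipids and glucose are not survey outcomes, so those two drug classes concern only the trial's exposure analyses.

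**2. Illustration of size.** The protocol gives no treatment rate, drug effect or exposure slope, so there is no stated figure to reproduce. Every input below is an assumption.

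- Untreated systolic pressure: mean 130 mmHg, residual SD 16, true slope b = 2 mmHg per SD of exposure.
- A share t of people at or above 140 mmHg is treated (30% to 70%), and treatment lowers the reading by L (5 to 15 mmHg).
- Recorded value = untreated value − L × (1 if treated, 0 if not).

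For normally distributed exposure, the recorded slope divided by the true slope is

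ratio = 1 − t × L × f, with f = φ(c)/S, S = √(16² + 2²) = 16.12 and c = (140 − 130)/16.12 = 0.620.

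φ(0.620) = 0.329, so f = 0.329/16.12 = 0.0204 per mmHg.

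- t = 0.3, L = 5: 1 − 1.5 × 0.0204 = 0.97, a loss of 3%.
- t = 0.5, L = 10: 1 − 5 × 0.0204 = 0.90, a loss of 10%.
- t = 0.7, L = 15: 1 − 10.5 × 0.0204 = 0.79, a loss of 21%.

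Simulation with 400,000 people gives the same ratios (0.97, 0.90 and 0.79). With mean 132, SD 17 and slope 2, f = 0.0209, and the last case becomes 1 − 10.5 × 0.0209 = 0.78, a loss of 22%. The range is therefore about 3% to 22%.

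**3. Share classed as raised (140 mmHg or more), first set of assumptions.** The true share is about 27%. Recorded readings alone give 24% (t = 0.3, L = 5) down to 12% (t = 0.7, L = 15). If every treated person reports the diagnosis and a case is a raised reading or a diagnosis, the share returns to about 27%.

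**4. Direction.** Step 2 lets treatment depend on pressure alone. Suppose instead that uptake among people with raised pressure changes by k per SD of exposure. The treated share then has an added slope of about k × 0.268, where 0.268 is the share with raised pressure. At t = 0.5 the attenuation is cancelled when

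k = −(0.5 × 2 × 0.0204)/0.268 = −0.076.

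If uptake falls by about 8 percentage points per SD of exposure, the loss disappears, and a steeper fall reverses the sign of the bias. If uptake rises with exposure, the loss grows.

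**The case against.** The strongest reply is that the survey does ask for physician-diagnosed disease. A reader might infer from the missing medication item that the plan counts medicated people as healthy. The documents do not support that: no section says so, and a treated person who reports hypertension is recorded as having it. The method named in Section 8 is logistic regression, which suggests binary outcomes, and for these the diagnosis item can repair much of the problem (step 3). This stands. It does not dispose of the point, because the repair needs complete reporting and a case definition that uses the diagnosis. A diagnosis also does not separate treated from untreated people, so a continuous reading still cannot be corrected.

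The size rests wholly on assumed inputs, and its low end is small. The roughly 40% with cardiovascular disease cited in Section 6 is not a treatment rate. Both remarks are fair.

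A reader might also extend the point to lipid and glucose drugs in the survey, or to the comparison of trial arms. Neither extension holds: lipids and glucose are not survey outcomes, and randomisation balances baseline medication between arms on average.

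Section 18 says only what the data will include, the questionnaire is not shown, and Section 8 has researchers review health status at the first trial visit. Medication might be asked in practice. But this is the section that sets out the data types, down to feedback on the study, so reading the absence as an omission is fair. Case definitions may properly sit in an analysis plan; the missing data item cannot be supplied there.

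Finally, Section 18 refers to identifiable data from the anonymous survey, so it is not certain that respondents could never be reached again. The protocol does not plan such contact, except with those who volunteer for the trial.

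**Conclusion.** The point holds in a limited form. Treatment for raised blood pressure is not a listed survey item, although blood pressure is a primary-endpoint outcome of a non-randomised, one-time survey. Treated readings cannot be corrected, and attenuation of the exposure association is the likely result. For a linear slope the illustrative loss is about 3% to 22%. That range assumes that treatment depends only on pressure, that 30% to 70% of people at or above 140 mmHg are treated, and that treatment lowers the reading by 5 to 15 mmHg. Bias toward zero is likely but not certain, since uptake may vary with exposure or socioeconomic status. For a binary outcome the diagnosis item can remove much of the bias if it is used. In the trial, unlisted lipid- and glucose-lowering treatment weakens the exposure analyses of HDL, triglycerides and glucose, but not the comparison of arms on average.

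**What to change.** - Add to the survey, and to the list in Section 18, one yes/no item on current blood-pressure-lowering medication.
- Record current blood-pressure-, lipid- and glucose-lowering medication at the trial's Day 1 visit.
- In the exposure analyses, define elevated blood pressure as a raised reading or current treatment. For continuous blood pressure, add a sensitivity analysis that corrects treated values or handles them as censored.
- If the survey has already been fielded, use raised reading or physician-diagnosed hypertension as the outcome or as a sensitivity analysis, and state the limitation for continuous readings. Recording at Day 1 remains possible for trial participants not yet seen.

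The cost is a slightly longer questionnaire, a short entry on the Day 1 form and a small addition to the analysis.
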